#### 10.4.4 General guidelines for reporting adverse events

- AEs are to be recorded in corresponding screen(s) included in the eCRF.
- The reporting requirement of AEs depends on patient status (study completer or patient who had premature permanent discontinuation of IMP)
  - In patients who receive IMP until the end of the study (study completer), all AEs, regardless of seriousness or relationship to IMP/NIMP, spanning from the signature of the informed consent form until the CSED visit are to be recorded in the eCRF. Patients who experience a new or ongoing related or serious AE or a new or ongoing AESI (see [Section 10.4.2](#)) at the CSED visit should be followed beyond the CSED visit until resolution, stabilization, or death (whichever comes first) and related data will be collected (see [Section 10.1.5.4.1](#)).
  - In patients who have permanent premature IMP discontinuation:
    - All AEs, regardless of seriousness or relationship to IMP/NIMP, spanning from the signature of the informed consent form until 6 months following V70 (end of treatment visit) are to be recorded in the eCRF.
    - From 6 months following V70 until the CSED visit, related and/or serious AEs should be recorded in the eCRF.

***NOTE:** Reporting requirement for suspected efficacy endpoints is the same regardless of patient status (study completers or patients who had premature permanent discontinuation of IMP); suspected efficacy endpoints should be reported in all randomized patients until the end of the study (CSED).*

- Whenever possible, diagnosis or single syndrome should be reported instead of symptoms. The Investigator should specify the date of onset, intensity, action taken with respect to IMP, corrective treatment/therapy given, additional investigations performed, outcome, and his/her opinion as to whether there is a reasonable possibility that the AE was caused by the IMP.
- When treatment is prematurely discontinued, the patient will be maintained in the study and the patient's observations will continue until the common study end date visit (see [Section 10.3.4](#)).
- Laboratory, vital signs or ECG abnormalities are to be recorded as AEs only if:
  - Symptomatic and/or
  - Requiring either corrective treatment or consultation, and/or
  - Leading to IMP discontinuation or modification of dosing (with exception of LDL-C levels which may lead to IMP dosing modification, but in a blinded manner), and/or
  - Considered as clinically relevant (such as for ECG a prolonged QTcB > 500 ms or an increase in QTcB of > 60 msec compared to baseline), and/or
  - Fulfilling a seriousness criterion, and/or
  - Defined as an AE of special interest with immediate notification

See [Appendix E](#) for a summary of AE and efficacy endpoint reporting guidelines.

#### 10.4.5 Instructions for reporting serious adverse events

In the case of occurrence of an SAE, the Investigator must immediately:

- ENTER (within 24 hours) the information related to the SAE in the appropriate screens of the eCRF; the system will automatically send a notification to a representative of the pharmacovigilance team after approval of the Investigator within the eCRF or after a standard time has elapsed, whichever comes first. Transmission to the pharmacovigilance team of information related to the SAE will be done either by fax or with an electronic solution.
- SEND (preferably by fax or e-mail) a photocopy of all examinations carried out and the dates on which these examinations were performed, to a representative of the pharmacovigilance team whose name, fax number, and email address will be provided for each region in a separate document. Care should be taken to ensure that the patient's identity is protected and the patient's identifiers in the clinical trial are properly mentioned on any copy of a source document provided to the Sponsor. For laboratory results, include the laboratory normal ranges.
- All further data updates should be recorded in the eCRF as appropriate, and further documentation as well as additional information (for laboratory data, concomitant medications, patient status, etc) should be sent (by fax or e-mail) to a representative of the pharmacovigilance team within 24 hours of knowledge of the SAE. In addition, every effort should be made to further document any SAE that is fatal or life threatening within a week (7 days) of the initial notification.
- A back-up plan (using a paper CRF process) is available and should be used when the eCRF system does not work.

#### 10.4.6 Guidelines for reporting adverse events of special interest

##### 10.4.6.1 Reporting of adverse events of special interest with immediate notification

For these AEs, the Sponsor will be informed immediately (ie within 24 hours), as per SAEs notification described in [Section 10.4.5](#), even if not fulfilling a seriousness criterion, using the corresponding screens in the eCRF.

- ALT  $\geq 3$  ULN (if baseline ALT < ULN) Or ALT  $\geq 2$  times the baseline value (if baseline ALT  $\geq$  ULN) (Please refer to related flowchart in [Appendix C](#)).
- Allergic events
  - Allergic drug reactions and/or local injection site reactions deemed to be allergic (or have an allergic component) that require consultation with another physician for further evaluation of hypersensitivity/allergy, as per the investigator's medical judgment or as per [Section 10.6.2](#), should be reported as an AESI with immediate notification.
  - All allergic events, and all injection site reactions having an allergic component or deemed to be allergic, require completion of the specific eCRF screen (see [Section 10.6.2](#)), regardless of requirements for immediate reporting.

- Hemolytic anemia (see [Section 10.4.7.1](#) and [Appendix D](#))
  - If there is a decrease in hemoglobin and reflexive testing as per [Appendix D](#) suggesting hemolysis, then report this as an AESI with immediate notification. Special eCRF screen will need to be completed
- Pregnancy
  - *Pregnancy occurring in a female patient enrolled in the study* will be recorded as a pre-specified AE with immediate notification in all cases, and IMP should be discontinued in all cases. It will be qualified as an SAE only if it fulfills the SAE criteria. The follow-up of the pregnancy will be mandatory until the outcome of the pregnancy has been determined.
  - *Pregnancy occurring in the female partner of a male patient included in the clinical trial*: if permitted by the female partner and by local regulatory policies, it will be recorded as a pre-specified AE with immediate notification (SAE if it fulfills the SAE criteria), and pregnancy should be followed-up until the outcome has been determined.
- Symptomatic Overdose with IMP
  - An overdose (accidental or intentional) is an event suspected by the Investigator or spontaneously notified by the patient (not based on systematic injection counts) and defined as at least twice of the intended dose within the intended therapeutic interval (ie, 2 or more injections from the double-blind treatment kit are administered in <7 calendar days); to be reported using the corresponding screens in the eCRF using the Term “symptomatic OVERDOSE (accidental [or intentional])”. The patient should be monitored and appropriate symptomatic treatment instituted
  - The circumstances of the overdose should be clearly specified in the verbatim
- Neurologic and Neurocognitive Events
  - Neurologic and Neurocognitive Events that require additional examinations/procedures and/or referral to a specialist should be reported as an AESI with immediate notification (see also [Appendix E](#) for reporting requirements).

#### **10.4.6.2 Reporting of adverse events of special interest without immediate notification**

See [Appendix E](#).

For these AEs, the Sponsor does not have to be informed immediately, unless meeting seriousness criterion.

- Asymptomatic overdose with IMP
  - An overdose (accidental or intentional) is an event suspected by the Investigator or spontaneously notified by the patient (not based on systematic injection counts) and defined as at least twice of the intended dose within the intended therapeutic interval (ie, 2 or more injections from the double-blind treatment kit are administered in <7 calendar days); to be reported using the corresponding screens in the eCRF using

the Term “asymptomatic OVERDOSE (accidental [or intentional])” The patient should be monitored for any AEs and treated, as needed

- Local injection site reactions (see [Section 10.6.1](#))
  - Local injection site reactions related to IMP that are considered as non-allergic events should be further characterized by evaluating the related symptoms that comprise an injection site reaction such as but not limited to redness, pain, etc (See [Appendix F](#)). Special eCRF screens will need to be completed. If such an AE was to occur, then do not report the individual components of the reaction but rather the term “local injection site reaction”, the individual components being described in the specific eCRF screen
- Allergic events not referred for consultation with another physician (see [Section 10.4.6.1](#))
  - All allergic events will need to have allergy specific eCRF screens completed (see [Section 10.6.2](#)), regardless of requirements for immediate reporting.
- Neurologic and Neurocognitive events
  - AEs related to neurologic or neurocognitive abnormalities with the exception of those requiring additional examinations/procedures and/or referral to a specialist (as mentioned in [Section 10.4.6.1](#)) should be reported in accordance with [Appendix E](#).

#### 10.4.7 Guidelines for management of specific laboratory abnormalities

Laboratory abnormalities with pre-specified monitoring should be monitored, documented, and managed according to the related flowchart in protocol [Appendix C](#) and [Appendix D](#)

- Neutropenia
- Thrombocytopenia
- Increase in ALT
- Acute renal insufficiency
- Decrease in hemoglobin (defined as  $\geq 1.5$  g/dL decrease from pre-randomization baseline value)
- Increase in CPK (other than cardiac-related) and suspicion of rhabdomyolysis.

Investigators are strongly encouraged to follow these algorithms in [Appendix C](#) and [Appendix D](#), especially in situations where the abnormality persists or when there is no clear explanation for the observed abnormality.

However there may be situations where these algorithms are not entirely applicable, therefore Investigator may use his/her best judgment. Also, in some situations, the Sponsor may wish to discuss with the Investigator. Examples where these algorithms may not be applicable include (but are not limited to) the following situations:

- patients with known stable low or borderline neutrophil or platelet count or impaired renal function at baseline; Investigator should attempt to have a diagnosis for the observed finding and should use his/her best judgment whether or not to enroll these patients, and if

patient is enrolled, on how to best monitor these baseline abnormalities throughout the study

- patients with ALT increase or elevated CK for which the abnormality resolves following statin dose reduction or statin discontinuation
- patients with elevated CK caused by a myocardial infarction

In addition, discontinuation caused by a laboratory abnormality can be either permanent or temporary, depending on the particular case. There is no requirement for permanent treatment discontinuation in every case of the general guidance for the follow up of selected laboratory abnormalities mentioned in [Appendix C](#).

#### **10.4.7.1 Hemoglobin decrease**

See [Appendix D](#).

At the first post-randomization study visit with occurrence of a hemoglobin (Hb) measurement decrease by  $\geq 1.5$  g/dL as compared to the randomization visit hemoglobin measurement, then the Central Lab will reflexively measure haptoglobin using specimens already obtained at the same time point for which the hemoglobin decrease was detected. The Central Lab will then provide the results of the reticulocyte count, haptoglobin, LDH and indirect bilirubin (reflexively measured only if the total bilirubin  $>$  ULN) to the Investigator.

***NOTE:** At selected sites with a longer transit time to Central Lab where reticulocyte count cannot be measured by Central Lab, a second hematology sample will be collected for local assessment of reticulocyte count,*

- If the following pattern of abnormalities is noted:
  - Reticulocyte count  $>$  Central Lab (or if applicable, local lab) upper limit of the reference range (also referred to as ULN) **AND**
  - Haptoglobin  $<$  Central Lab's lower limit of the reference range (also referred to as LLN) **AND**
  - LDH  $>$  ULN **AND**
  - Indirect bilirubin  $>$  ULN (only if the total bilirubin  $>$  ULN)

The patient should be referred to a hematologist. The hematologist should obtain a peripheral blood smear and anti-erythrocyte antibodies (direct and indirect) by Coombs test. Further investigations are at the discretion of the hematologist.

- If the results are normal or the pattern of abnormality is something other than that described above, then the Investigator should exercise his/her medical judgment in the interpretation of the results, necessity for workup of the decrease in hemoglobin or referral to a hematologist

If a second hemoglobin measurement demonstrating a further decrease of  $\geq 1$  g/dL from the last available value is observed, even if the previous work-up was negative, the same investigations can be repeated and a hematology consultation can be requested at the discretion of the Investigator or at the Sponsor's request.

## 10.5 OBLIGATIONS OF THE SPONSOR

During the course of the study, the Sponsor will report in an expedited manner all SAEs that are both unexpected and at least reasonably related to the IMP (Suspected Unexpected Serious Adverse Reaction[SUSAR]), to the Health Authorities, IECs/IRBs as appropriate and to the Investigators.

In addition, the Sponsor will report in an expedited manner all SAEs that are expected and at least reasonably related to the IMP to the Health Authorities, according to local regulations.

In this study, cardiovascular efficacy endpoints specified (primary and secondary efficacy endpoints) are waived from expedited reporting to Health Authorities providing an agreement has been reached with them.

Also some other AEs may be considered related to the underlying condition and thus will not be considered unexpected as given in the Investigator's Brochure.

Any other AE not listed as an expected event in the Investigator's Brochure or in this protocol will be considered as unexpected.

The Sponsor will report all safety observations made during the conduct of the trial in the clinical study report (CSR).

## 10.6 SAFETY INSTRUCTIONS

### 10.6.1 Local tolerability (Local Injection Site Reactions)

In case the Investigator or the patient recognizes any signs of local intolerability, then this should be treated and followed up as per the Investigator's medical judgment. See [Section 10.4.6.2](#) and [Appendix F](#) for further information.

### 10.6.2 Allergic adverse events (See [Section 10.4.6.1](#) and [Section 10.4.6.2](#))

Specific eCRF screens are to be filled in to assess allergic reactions or allergic-like reactions that may occur during the clinical studies conducted with alirocumab.

Sometimes transient injection site reactions, irritant in nature, may occur, requiring no intervention and being of dubious significance. These reactions would not be considered to be allergic reactions.

Adverse events that may constitute an allergic reaction (eg, generalized itch, nasal itch, swelling at injection site, flushing, hives, swelling at lips, eyes, face, tongue, hands, feet, lump in throat, difficulty to swallow, hoarseness, change in pitch of voice, incapacity to speak, wheezing, chest tightness, stridor, etc) should be considered to be reported on the General Allergic Reaction and/or Local Injection Site Reaction Complementary Form.

Adverse events that are obviously not of allergic origin (eg, local injection site reactions related to IMP and with no allergic component) should only be recorded on the Local Injection Site

Reaction Complementary Form. However, injection site reactions which progress/expand/worsen/etc should be evaluated as recommended in [Section 10.6.2.1](#) and General Allergic Reaction Complementary form should be completed.

The IMP should be immediately interrupted (temporarily discontinued) if there is a suspicion of an allergic event related to IMP. See [Section 10.3.1](#) for further information on treatment interruption and [Section 10.3.2](#) for criteria for permanent treatment discontinuation.

#### **10.6.2.1 Allergic adverse event with cutaneous involvement**

Adverse events with cutaneous involvement which are obviously of allergic origin or injection site reactions which progress/expand/worsen/etc should be evaluated by a dermatologist as soon as possible, and preferably within one week of the site first becoming aware of the event.

The investigator should evaluate the patient for possible etiologies (new medications, etc) and extra-cutaneous symptoms and signs. An unscheduled Central Laboratory assessment for hematology, chemistry, liver panel, and ADA should be obtained. If it is possible, the site will take pictures of the skin lesions in order to provide the patient with them for the dermatologist's visit. If the photos are obtained, then copies should be kept as source documents which may later be collected by the sponsor. The investigator will provide a summary of the patient's case, reason for consultation, and information being requested to the consulting dermatologist.

A full consultation report should be sent by the dermatologist to the investigator. The full report should contain, at a minimum, the following information; a detailed description of the rash (such as the morphology [lesion type], shape of individual lesions, arrangement of multiple lesions [eg, scattered, grouped, linear, etc], distribution, color, consistency, presence of pruritus or pain, and other clinical signs) and in case a skin biopsy (including histopathology and immunofluorescence) was done (if it was deemed necessary as per the dermatologist's or investigator's medical judgment), the results of this investigation with, if applicable, a specific diagnosis of the AE. The investigator will fax the full report and the corrected AE form if necessary, to the Monitoring Team Representative within 24 hours.

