## 6.1 DESCRIPTION OF THE PROTOCOL

The study will comprise 2 periods:

- A run-in period (~ 2 to 16 weeks) during which the background lipid-modifying therapy (LMT) will be adjusted as needed, to ascertain the patient is receiving the required intensive statin treatment (defined as atorvastatin 40 or 80 mg, or rosuvastatin 20 or 40 mg) or the maximally tolerated doses of these given statins, or other non-statin LMTs prior to randomization, and to stabilize this treatment.
- A double-blind treatment period (~ 2 to 5 years) during which the following should be emphasized and reinforced:
  - *compliance with study visits and assessments*: all randomized patients (including those who permanently discontinued treatment early) must remain in the study and be followed until the end of the study; sites should maintain a contact with the patient every 2 to 3 months (as per study assessments) throughout the study and contact information (for patient, family, GP/cardiologist) should be periodically updated as necessary; in addition, it is important to continuously remind patients (and their family) throughout the study that, in case of hospitalization, patient (or patient's family member) should inform site (Investigator, Coordinator) as soon as possible and not wait until the next visit.
  - *compliance with blinded study treatment (IMP)*: patients should be treated with blinded study treatment for as long as possible, unless safety concerns arise (in case of temporary interruption, blinded study treatment should be restarted, as best as possible, unless there are safety concerns; to be assessed by Investigator)
  - *compliance with required background LMT regimen* (as determined from run-in period see [Section 6.1.1](#)): intensive statin therapy (atorvastatin 40 or 80 mg or rosuvastatin 20 or 40 mg) or maximal tolerated dose of one these 2 statins, optimized with addition of non-statin LMTs (at Investigator's discretion) should be continued for as long as this regimen remains well tolerated. If tolerability concerns arise, LMT can be modified, based on clinical tolerability only (see [Figure 2](#), [Section 8.8.1](#))

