3.1.5.4 Patients with LDL-C <25 mg/dL (0.65 mmol/L)

The assessment will include:

- The proportion of patients with two consecutive results, spaced out by at least 21 days, of LDL-C <25 mg/dL (<0.65 mmol/L) (respectively LDL-C <15 mg/dL, ie, <0.39 mmol/L) during the double-blind treatment period
- The time to the first LDL-C <25 mg/dL (respectively LDL-C <15 mg/dL) for these patients.

In case both calculated and measured LDL-C are provided for the same sampling, the measured LDL-C will be considered.

3.1.5.5 Anti-alirocumab antibodies assessed throughout the study.

Anti-alirocumab antibodies (ADAs) are assessed at Visit 3 (Month 0), Visit 5 (Month 2), Visit 6 (Month 4), and Visit 10 (Month 12) for the first year, then every year and at the final on-treatment visit (CSED visit for completers, or early end of treatment visit for patients who discontinued the treatment).

ADA measurements will be assigned to analysis windows as defined in Section 3.5.4.

The following variables will be described:

- ADA response (Positive or Negative). For ADA positive:
 - Titer levels
 - Neutralizing status (Positive or Negative)
- Pre-existing positive ADA defined as patients with positive ADA response at baseline with less than 4-fold increase in titer in the post-baseline period
- Treatment-emergent positive ADA response defined as 1) Patients with no ADA positive response at baseline but with any positive response in the post-baseline period (up to follow-up visit) or 2) Patients with a positive ADA response at baseline and at least a 4-fold increase in titer in the post-baseline period (up to follow-up visit). For treatment-emergent positive ADA, the following categories for ADA duration will be applied:
 - A persistent positive response is a treatment-emergent ADA positive response detected in at least 2 consecutive post-baseline samples separated by at least a 16-week period
 - An indeterminate duration positive response is defined as ADA present only at the last sampling time point
 - A transient positive response is defined as any treatment-emergent positive ADA response that is neither considered persistent nor indeterminate

In addition, potential ADA samples that are to be collected after CSED visit for patients with titer \geq 240 at CSED visit will be listed.

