The time to the first TEAE/event will be compared for patients with 2 consecutive LDL-C <25 mg/dL versus $\geq 25 \text{ mg/dL}$, within the alirocumab group, using a Cox model, including the covariate for 2 consecutive LDL C <25 mg/dL (Yes/No). Hazard ratio (and 95% CI) from this model will be provided. The event rate per 100 patient-years (the number of patients with an event in question divided by total 100 patient-years) will also be provided.

Second screening approach

TEAE summary by primary SOC, HLGT, HLT, and PT as well as groupings of events (ie, cataract, neurological events, neurocognitive disorders and "new onset of diabetes" will be provided on the safety population according to baseline LDL-C categories (eg, <70, ≥70 to <90, ≥90 to <110, ≥110 mg/dL).

Hazard ratio (and 95% CI) for alirocumab effect versus placebo within each baseline LDL-C subgroup will be provided using a Cox model with baseline LDL-C (in categories), treatment group and the treatment-by-baseline LDL-C interaction term.

To assess the impact of baseline LDL-C on hazard ratio, a Cox model including the baseline LDL-C (as continuous factor), treatment group and treatment-by-baseline LDL-C interaction term will be used. The p-value from the interaction term will be provided for descriptive purpose to evaluate if there is a potential relationship between baseline LDL-C and hazard ratio.

Second step

For each pre-specified event (cataract, neurological events, neurocognitive disorders, new onset of diabetes) as well as for each event with a potential signal detected in the first step, the time to the first TEAE/event will be compared for patients with 2 consecutive LDL-C <25 mg/dL versus \geq 25 mg/dL, within the alirocumab group, using a Cox model, including the covariate for 2 consecutive LDL-C <25 mg/dL (Yes/No) and prognostic factors of the event analyzed. Adjusted HR (and 95% CI) from this model will be provided.

The list of prognostic factors will be established based on the literature and on study data (as applicable).

Subgroups of patients with treatment-emergent ADA positive response

All TEAEs by primary SOC, HLGT, HLT, and PT as well as local injection site reactions will be described in the alirocumab group according to the following ADA parameters:

- Treatment-emergent ADA positive response (yes/no)
- Persistent/transient/indeterminate treatment-emergent ADA positive response.

Analysis of all treatment-emergent serious adverse event(s)

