3.4.7.5 Analyses of anti-alirocumab antibody variables

The following summaries will be performed on the ADA population, taking into account all samples regardless of timing in relation to injections. ADA results will be summarized by treatment group and up-titration status (see Section 3.4.5).

- ADA results (negative or positive) by time point;
- Neutralizing status (negative or positive) by time point for positive ADA;
- ADA titers using descriptive statistics (median, minimum, and maximum) for positive ADA by time point;
- Number (%) of patients with pre-existing ADA and number (%) of patients with treatment-emergent ADA positive response;
- Number (%) of patients with persistent/transient/indeterminate treatment-emergent ADA positive response;
- Time to onset of treatment-emergent ADA positive response using descriptive statistics;

- 11-Oct-2017 Version number: 3
- Number (%) of patients with at least 1 neutralizing ADA.

Correlations between ADA parameters (eg, titers, treatment-emergent ADA positive status, neutralizing status), safety and/or efficacy endpoints will be also explored (eg, scatter plot).

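### Reaction-triggered antibody samples count towards ADA status, which tilts the descriptive reaction-by-ADA tables slightly upward; a scheduled-samples version should stand beside them

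*Protocol*

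**What the plan says.** **When the extra sample is taken.** Protocol 10.6.2.1 applies to a defined group: skin events that are plainly allergic, and local reactions at the injection site that spread or get worse. For them, "An unscheduled Central Laboratory assessment for hematology, chemistry, liver panel, and ADA should be obtained". The neighbouring sections on local tolerability (10.6.1) and acute allergic injection reactions (10.6.2.2) ask for no ADA sample.

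**Everyone else.** SAP 3.1.5.5 fixes the planned visits; samples "are assessed at Visit 3 (Month 0), Visit 5 (Month 2), Visit 6 (Month 4), and Visit 10 (Month 12) for the first year". After that they are annual, with one more at the last on-treatment visit. For patients who stop early, that last visit is V70.

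**How status is assigned.** SAP 3.1.5.5 defines treatment-emergent positivity in two ways. The first is "Patients with no ADA positive response at baseline but with any positive response in the post-baseline period". The second, for patients already positive at baseline, requires at least a 4-fold titer rise. Persistent status needs two consecutive positives at least 16 weeks apart. Indeterminate means positive only at the last sampling point, and transient is the remainder.

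**Which samples enter.** The general rule at the head of SAP 3.4.7, which covers the ADA section, takes in scheduled and unscheduled measurements alike. SAP 3.4.7.5 adds that ADA summaries are made "taking into account all samples regardless of timing in relation to injections".

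**Where status meets reactions.** SAP 3.4.5.1 tabulates all TEAEs by ADA status, and likewise "local injection site reactions will be described in the alirocumab group according to the following ADA parameters". Two splits are given: yes/no for a treatment-emergent response, and its duration class (persistent, transient or indeterminate).

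**The concern.** The exposure variable in these tables (ADA status) is measured more often in patients who have the outcome (a reaction). That is detection bias: each extra test is another chance to be called positive, so reactors are over-represented among ADA positives even if antibodies and reactions are unrelated. The direction is known in advance. It is a separate matter from whether the antibody came before or after the event.

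Antibody development is a secondary objective (Protocol 5.2, SAP 1.2.2). Allergic events and injection-site reactions are events of special interest handled as Tier 1 (SAP 3.1.4.1, 3.4.5.1). A modest excess of reactions among ADA-positive patients could therefore be read as an immunogenicity signal when part of it comes from the sampling rule.

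**Working it through.** The plan states no figure for this analysis, so there is nothing to reproduce. The check is the size of the artefact when reactions and ADA are independent.

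**Inputs from the documents.** One unscheduled ADA sample per triggering event (Protocol 10.6.2.1). Scheduled post-baseline samples (SAP 3.1.5.5): M2, M4, M12, M24 = 4 at 24 months; adding M36, M48, M60 and the final visit at M64 = 8.

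**Assumptions, not in the documents.** Positivity per sample p = 0.2% to 5%; 4% of patients have a reaction; 100%, 50% or 10% of reactors receive the extra sample.

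**Step 1: independent samples.** P(ADA+) = 1 − (1 − p)^k without the extra sample and 1 − (1 − p)^(k+1) with it. For k = 4 and p = 1%:

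- without: 1 − 0.99^4 = 3.94%
- with: 1 − 0.99^5 = 4.90%, so the chance of being called positive is multiplied by 1.24

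**Step 2: what the table would show.** Still with k = 4 and p = 1%, and every reactor sampled:

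- overall ADA+ = 0.04 × 4.90% + 0.96 × 3.94% = 3.98%
- reactions among ADA+ = 0.04 × 4.90% / 3.98% = 4.93%
- reactions among ADA− = 0.04 × 95.10% / 96.02% = 3.96%
- ratio 1.24

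With half of reactors sampled the rates are 4.47% and 3.98% (1.12). With a tenth they are 4.09% and 4.00% (1.02).

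Across p = 0.2% to 5%:

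| Scheduled samples | Chance of ADA+ multiplied by | Reaction ratio, all reactors sampled | Half | A tenth |
|---|---|---|---|---|
| 3 | 1.30–1.33 | 1.32–1.35 | 1.16–1.17 | 1.03 |
| 4 | 1.22–1.25 | 1.24–1.27 | 1.12–1.13 | 1.02–1.03 |
| 5 | 1.17–1.20 | 1.19–1.22 | 1.10–1.11 | 1.02 |
| 8 | 1.10–1.12 | 1.12–1.15 | 1.06–1.07 | 1.01 |

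**Step 3: antibodies that persist.** Independence is the extreme case. A simulation placed one antibody episode of fixed length, and one triggered sample, at random times on the actual schedule. The multiplier on the chance of being called positive was:

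| Episode length | 24 months of follow-up | 64 months of follow-up |
|---|---|---|
| 1 month | 1.21 | 1.11 |
| 4 months | 1.17 | 1.08 |
| 8 months | 1.07 | 1.04 |
| 12 months or more | 1.00 | 1.00 |

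The last row follows from the schedule: its longest gap is 12 months, so it already catches every such episode.

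**Step 4: between arms.** If 4% of alirocumab patients react, all are sampled, and placebo has no reactors, arm-level ADA incidence rises by 0.04 × (4.90% − 3.94%) = about 0.04 percentage points.

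**Step 5: scheduled samples only.** Reactors and non-reactors with equal follow-up then have equal numbers of tests, and the ratio under the null is 1.00.

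**The case against.** **Perhaps triggered samples do not count.** SAP 3.5.5 lists the data for which unscheduled values may be used and ADA is not among them. SAP 3.1.5.5 names scheduled visits and assigns ADA to analysis windows, which cover only part of follow-up. The phrase in 3.4.7.5 is about timing relative to injections. No single sentence says that a triggered ADA sample sets the yes/no status. This does not carry, however. SAP 3.5.5 permits and does not exclude; SAP 3.4.7 expressly takes in unscheduled measurements; and the windows in 3.5.4 serve summaries by time point, whereas treatment-emergent status is defined over the whole post-baseline period.

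**The trigger is narrow.** This stands. The tables cover all TEAEs and all local injection-site reactions, most kinds of which prompt no extra sample, so the effect is diluted. The documents do not give the share of reactors who would be sampled.

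**Other rules limit the damage.** This partly stands. Baseline-positive patients need a 4-fold titer rise, and one isolated triggered positive cannot make a patient persistent. But an inserted sample can change which samples are consecutive or last, so the three duration classes are not fully protected.

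**V70 also adds a test.** True, but it does not offset the bias. Some hypersensitivity and injection reactions are themselves reasons to stop treatment (Protocol 10.3.3), so V70 can be reaction-linked too.

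**Scheduled-only status loses information.** This stands. It drops the sample nearest the reaction, may miss short-lived antibodies present at the event, and could weaken a true association. That argues for showing both versions and against replacing one by the other.

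**Conclusion.** The bias is real, small and upward. One extra sample gives a spurious ratio of about 1.0 to 1.25 with 4 to 8 scheduled samples, touching 1.27 at 5% positivity with 4 samples and every reactor sampled. It shrinks as fewer reactors meet the trigger and vanishes for antibodies lasting 12 months or more. These sizes rest on assumed positivity and reaction rates.

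A reader might go further in four ways that the documents do not support:

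- **That all allergic or local reactions bring an extra test.** Only obviously allergic cutaneous events and worsening injection-site reactions do.
- **That any reaction–antibody association found here would be a testing artefact.** One extra sample cannot produce a ratio well above the range shown (up to 1.35 with only 3 scheduled samples). Ratios of 1.35 to 1.55 need two extra samples and independent results, hence repeat triggering events.
- **That alirocumab's ADA incidence would be materially inflated against placebo.** The effect is about 0.04 percentage points, and SAP 3.4.7.5 plans summaries by group, not a test.
- **That the trial's conclusions are at risk.** The tables are descriptive and within one arm; the primary and main secondary analyses are untouched.

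This is a cheap improvement to a secondary safety display.

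**What to change.** In SAP 3.4.5.1 and 3.4.7.5:

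- Show the reaction-by-ADA tables, both yes/no and persistent/transient/indeterminate, with ADA status derived from protocol-scheduled samples only, beside the all-samples version.
- State how the V70 sample is treated in the scheduled-only version.
- List each sample taken under Protocol 10.6.2.1 with its result and the event that prompted it.

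Sampling at sites does not change. The cost is a few sentences in the SAP, a scheduled/unscheduled flag on the ADA records and one extra set of tables. The scheduled-only version can miss transient antibodies present only at the event; keeping the all-samples version and the listing ensures that no safety information is lost.
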